2.2.1 Randomization and drug dispensing irregularities

Randomization and drug-dispensing irregularities occur whenever:

1. A randomization is not in accordance with the protocol-defined randomization method, such as a) an ineligible patient is randomized, b) a patient is randomized based on an incorrect stratum, c) a patient is randomized twice, or d) in a dynamic randomization scheme the treatment assignment is, in fact, not random, due to a computer program error.

OR

2. A patient is dispensed an IMP kit not allocated by the protocol-defined randomization, such as a) a patient at any time in the study is dispensed a different treatment kit than as randomized (which may or may not contain the correct-as-randomized IMP), or b) a nonrandomized patient is treated with IMP reserved for randomized patients.

Randomization and drug-dispensing irregularities will be monitored throughout the study and reviewed on an ongoing basis.

All randomization and drug-dispensing irregularities will be documented in the clinical study report. If the number of irregularities is large enough to make a tabular summary useful, the irregularities will be categorized and summarized among randomized patients (number and percentages). Nonrandomized, treated patients will be described separately

Randomization and drug-dispensing irregularities to be prospectively identified include but are not limited to:

- Kit dispensation without IRT transaction
- Erroneous kit dispensation
- Kit not available
- Randomization by error
- Patient randomized twice
- Stratification error
- Patient switched to another site

2.3 ANALYSIS POPULATIONS

Patients treated without being randomized will not be considered randomized and will not be included in the PK/PD efficacy population.

For any patient randomized more than once, only the data associated with the first randomization will be used in any analysis population.

The primary analysis of the study will be performed using the PKPD efficacy population (see section 2.3.5).

2.3.1 Randomized population

The randomized population (described in Section 2.2) includes all randomized patients and will be analyzed according to the treatment allocated by randomization. Allocation of randomized treatment to included patients will be centrally performed by an IRT. A patient is considered as

randomized as soon as there is a treatment kit number allocated and recorded in the IRT database, regardless of whether the treatment kit was used or not. Patients allocated outside the IRT will not be taken into account in any of the analyses.

2.3.2 Efficacy populations

2.3.2.1 *Modified Intent-to-treat population*

The modified intent-to-treat (mITT) population includes all randomized patients who received the single administration of IMP, with parasitologically confirmed *P. falciparum* malaria at baseline, having parasitemia data post-randomization.

For analyses and displays, patients will be classified according to the randomized treatment regardless of actual treatment received.

2.3.2.2 *Per-protocol population*

The per-protocol (PP) is the population receiving at least the single administration of FQ 400mg/OZ439, with parasitologically confirmed malaria at baseline, having parasitemia data post-randomization in order to be evaluable for Day 28 ACPR, without major protocol violations possibly affecting efficacy outcome. Note PCR-corrected ACPR applies only to recrudescence i.e. patients with new infections are considered non-evaluable for the analysis of PCR-corrected ACPR see Section 2.1.4).

Parasitemia data for patients with rescue treatment started before the considered time point will be excluded from this time point until Day 28.

In case of vomiting or other reasons interrupting the administration of the complete dose, and if valid parasitemia data post-randomization available, then patients will be included in the PP population.

As defined in [Section 2.1.4.1](#), there are certain criteria that would exclude patients from having an evaluable PCR-corrected ACPR at Day 28:

- Other species infection without *P. falciparum* reemergence,
- Lost to follow-up,
- Withdrawal,
- Protocol violation.

Protocol violations considered above are those potentially impacting efficacy assessments at Day 28:

- Patients who did not take IMP or who needed rescue treatment due to vomiting during IMP administration. Start of vomiting will be classified in 3 categories (< 5 minutes, [5-35] minutes, > 35 minutes and < 6 hours).
- Patient presenting severe malaria or receiving a rescue treatment due to severe malaria during the first 24 hours following IMP start (i.e. wrong inclusion).
- Start of rescue therapy before Day 28 assessment not due to: vomiting during IMP administration, wrong inclusion, treatment failure (per investigator or per WHO criteria), or other species infections.
- Missing baseline parasitemia, and positive parasitemia at 48 or 72 hours.
- Intermittent missing or out of window post-baseline parasitemia preventing to evaluate ACPR Day 28.
- Missing post-baseline body temperature preventing to evaluate ACPR Day 28.
- Out of Day 28 time window parasitemia preventing to evaluate ACPR Day 28.
- Patients who received treatment that differs from the randomized one.
- Patients re-dosed while they should not according to the protocol.
- Patients not re-dosed while they should have been according to the protocol.
- Patients with at least one enrolment violation among the following:
 - Patients who meet exclusion criteria E 01 which is: “Presence of severe malaria (according to WHO definition)”.
 - Patients violator for inclusion criteria I02 which is: “Presence of *P. falciparum* malaria, with a fever as defined with axillary temperature ≥ 37.5 degree Celsius ($^{\circ}\text{C}$) or oral/rectal/ tympanic temperature $\geq 38^{\circ}\text{C}$ or history of fever in the previous 24 hours (history of fever must be documented), with a mono-infection with *P. falciparum* and parasitemia (microscopically, blood smear) $\geq 3,000$ and $\leq 50,000$ asexual parasites/ μL of blood Microscopically (blood smear) confirmed parasite infection, ranging from 3000 to 50000 asexual parasites/ μL of blood”.
 - Patients violator for exclusion criteria E07 who would be treated with anti-malarial treatment:
 - from 6 weeks (with PQP-based compound, mefloquine, naphthoquine or sulphadoxine/pyrimethamine) before IMP administration,
 - 4 weeks (with amodiaquine or chloroquine) before IMP administration,
 - 14 days (quinine, halofantrine, lumefantrine-based compounds and any other anti-malarial treatment or antibiotics with antimalarial activity) before IMP administration,
 - 7 days (herbal products or traditional medicines) before IMP administration.

2.3.3 Safety population

The safety population is defined all patients who actually received at least 1 dose or part of a dose of the IMP. The Safety population will be analyzed according to the treatment actually received.

In addition:

- Randomized patients for whom it is unclear whether they took the IMP will be included in the safety population using treatment as randomized
- The OZ439 oral suspension should be discarded if the suspension limit time is exceeded. A new treatment kit box will need to be assigned to the patient via IWRs in order to prepare a new OZ439 oral suspension. The FQ capsules of the new treatment box will not be administered to the patient
- In case of OZ439 re-dosing mistake such as: erroneous kit dispensation at protocol planned re-dosing, protocol planned re-dose not performed, or re-dose performed wrongfully, the treatment group allocation for as-treated analysis will be the one closest to the sum of the administered total dose. Such cases will be tracked through quantitative deviations
- For patients erroneously re-dosed with FQ, the treatment group for as-treated analysis will be the one with the FQ dose the closest to the sum of the FQ dose actually administered to the patient. Such cases can only be tracked through qualitative deviations
- No re-dosing of FQ will be performed in case of vomiting during or after FQ administration but before OZ439 administration. In that case, OZ439 will not be administered and the patient will receive a rescue therapy as per section 7.7.1 of the study protocol. For patients mistakenly re-dosed with FQ, the treatment group for as-treated analysis will be the one with the FQ dose the closest to the sum of the FQ dose actually administered to the patient.

2.3.4 Pharmacokinetics population

The PK population includes all patients in the safety population with at least one evaluable blood sample for PK of either OZ439 or FQ post IMP administration and with adequate documentation of date of dosing and date of sampling.

2.3.5 Pharmacokinetics/pharmacodynamics populations

Two sub-populations will be defined, a PK/PD efficacy population and a PK/PD safety population:

2.3.5.1 PK/PD efficacy population

The PK/PD efficacy population will be the primary efficacy population.

Pharmacokinetic/pharmacodynamics (PK/PD efficacy) population will include those patients in both the PK and mITT populations with additional criteria specified below,..

Patients need at least one evaluable blood sample for PK of both OZ439 and FQ.

Parasitemia data for patients with rescue treatment started before the considered time point will be excluded from this time point until Day 28.

In case of vomiting or other reasons interrupting the administration of the complete dose, and if valid parasitemia data post-randomization available, then patients will be included in the PK/PD efficacy population.

As defined in [Section 2.1.4.1](#), there are certain criteria that would exclude patients from having an evaluable PCR-corrected ACPR at Day 28::

- Other species infection without *P. falciparum* reemergence
- Lost to follow-up,
- Withdrawal,
- Protocol violation.

Protocol violations considered above are those potentially impacting efficacy assessments at Day 28:

- Patients who needed rescue treatment because they did not take IMP or due to vomiting during IMP administration.
- Patient presenting severe malaria or receiving a rescue treatment due to severe malaria during the first 24 hours following IMP start (i.e. wrong inclusion).
- Start of rescue therapy before Day 28 assessment not due to: vomiting during IMP administration, wrong inclusion, treatment failure (per investigator or per WHO criteria), or other species infections.
- Missing baseline parasitemia, and positive parasitemia at 48 or 72 hours.
- Intermittent missing or out of window post-baseline parasitemia preventing to evaluate ACPR Day 28.
- Missing post-baseline body temperature preventing to evaluate ACPR Day 28.
- Out of Day 28 time window parasitemia preventing to evaluate ACPR Day 28.
- Patients with at least one enrolment violation among the following:
 - Patients who meet exclusion criteria E 01 which is: “Presence of severe malaria (according to WHO definition)”.
 - Patients violator for inclusion criteria I02 which is: “Presence of *P. falciparum* malaria, with a fever as defined with axillary temperature ≥ 37.5 degree Celsius ($^{\circ}\text{C}$) or oral/

rectal/ tympanic temperature $\geq 38^{\circ}\text{C}$ or history of fever in the previous 24 hours (history of fever must be documented), with a mono-infection with *P. falciparum* and parasitemia (microscopically, blood smear) $\geq 3,000$ and $\leq 50,000$ asexual parasites/ μL of blood Microscopically (blood smear) confirmed parasite infection, ranging from 3000 to 50000 asexual parasites/ μL of blood”.

- Patients violator for exclusion criteria E07 who would be treated with anti-malarial treatment:
 - from 6 weeks (with PQP-based compound, mefloquine, naphthoquine or sulphadoxine/pyrimethamine) before IMP administration,
 - 4 weeks (with amodiaquine or chloroquine) before IMP administration,
 - 14 days (quinine, halofantrine, lumefantrine-based compounds and any other anti-malarial treatment or antibiotics with antimalarial activity) before IMP administration,
 - 7 days (herbal products or traditional medicines) before IMP administration.

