AEs	←====	=====	-==	====	====		====		====	====		====	====	=====			=====	=====	=====	====	\Rightarrow	
Laboratory testing																						
Clinical laboratory safety ^h	Х											Х	(X)	(X)			Х		Х	Х	Х	72 and 96 h post-dose if participant still hospitalized

		Т	rea	tme	ent	Pe	rio	d a	nd p	ost-t	reatn	nent s	surve	illand	e (D	ays)		F	ollow	-up (Days)		
Procedure	Screening (up to 1					06	9					1		2	3	4	5	6	7	10	14	21	28 ±2	
Procedure	day before Day 0)										Ног	ırs po	st-dos	е					11	1	±1	± 2	±2	Notes
	,	0	1	2	4	6	8	3	12	18	24	30	36	48	72	96	120	144	168					
Visit	1 ^b					2						3		4	5	6	7	8	9	10	11	12	13 ^C	
Viral hepatitis serology	Х		1					-																rapid spot test (HAV IgM, HBsAg, HCV Ab), and/or HCV RNA (if known)
Pregnancy test	Х																						Х	Urine beta-HCG is the minimum acceptable test. Result must be confirmed negative prior to dosing.
PK OZ439 ^j		Х	Х	Χ	Х	Х			Х		Х			Х	Х		Х		Х		Х			Not measured in Arm A; Plasma samples
PK FQ (+metabolite) ^j		Х	Χ		Х	Х	()	X	Χ		Х				Х				Х		Х		Х	

- a Day 0 is defined as the day of single dose treatment to comply with WHO guidelines (2).
- b Visit 1 may occur on the same day as Visit 2 provided that all baseline assessments and biology results (including parasitemia and laboratory safety) are obtained before patient randomization.
- c In case of study discontinuation, all assessments planned on Day 28, including rescue therapy administration, should be performed as far as possible.
- d Administered at Day 28 for participants who reach Day 28 without having received a rescue medication. At each contact post-dosing, conditions for treatment failure will be assessed and rescue therapy will be given accordingly. See details in Section 7.7.1.

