10.2 POPULATIONS FOR ANALYSES

For purposes of analysis, the following populations are defined (Table 7):

Table 7 - Populations for analyses

Population	Description	
Screened participants	All participants who sign the ICF and met the inclusion criteria	
Randomized participants (intent to treat [ITT])	All participants with a treatment kit number allocated and recorded in IRT database at Visit 2 (Day 0), and regardless of whether the treatment kit was used or not	
Evaluable (modified ITT [mITT])	All randomized participants with parasitologically confirmed malaria at baseline, who received at least the single administration of OZ439/FQ 400 mg and who have parasitemia data post-randomization. Participants will be analyzed according to the treatment arm allocated by randomization	
Safety	All randomized participants who take at least 1 dose or part of a dose of the single administration OZ439 & FQ 400 mg. Participants will be analyzed according to the treatment they actually received	
PK	All participants included in the Safety population with at least one evaluable blood sample for PK post IMP administration and with adequate documentation of date of dosing and date of sampling	
PK/PD	All participants included in both the mITT population and the PK population	

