Baseline parasitemia was simulated for different scenarii, using truncated log-normal distributions. The base assumption was a baseline parasitemia greater than 1000 parasites/ μ L and of median about 10,000 parasites/ μ L. Some other scenarii were considered: baseline parasitemia greater than 3000, 5000, or 10,000 parasites/ μ L, with a maximum fixed at 5.5 log₁₀ parasites/ μ L. In the following, the baseline parasitemia greater than 3000 parasites/ μ L scenario was selected to ensure a better enrollment of patients during the study.

Based on N=10,000 simulations/arm and S=1000 simulations for the model parameters uncertainty, the results showed a PCR-corrected ACPR at Day 28 estimated at 72% (90%CI: [57% to 84%]) for FQ 400mg alone and 79% (90%CI: 67% to 87%) for FQ 600 mg alone for a baseline parasitemia greater than 3000 parasites/ μ L. Finally the FQ fixed dose of 400 mg was selected.

Results estimated that 30 evaluable participants per treatment arm will yield a power around 90% to detect an OZ439 concentration effect relation (in a population of patient with a baseline parasitemia greater than 3000 parasites/ μ L, for 4 arms FQ 400 mg + OZ439 at 0, 300, 600, and 1000 mg).

Part 2: Estimated power for various sample size of an OZ439 exposure-effect analysis, considering the fixed FQ dose, the 4 selected OZ439 dose levels (0, 300, 600, 1000 mg) and the selected baseline parasitemia

Simulation of clinical trials

Clinical trial simulations were used to simulate trials of 4 arms with a fixed dose of 400 mg FQ and 4 dose levels of OZ439 (0, 300, 600, and 1000 mg) for a baseline parasitemia greater than 3000 parasites/ μ L. FQ and OZ439 concentrations at Day 7 (168 h post dose) were simulated using log-normal distributions that were corrected to concentrations obtained from the FQ PopPK model and from the OZ439 PopPK model in an African adult population (as in part 1), and were assumed to be slightly correlated. Truncated log-normal distributions were used to simulate baseline parasitemia greater than 3000 parasites/ μ L in log₁₀Par/ μ L by a normal distribution:

mean=4, SD=0.55, minimum=3.48; maximum=5.5 (minimum and maximum for the truncation). Day 28 PCR-corrected ACPR was simulated using a “hypothetical” model linking ACPR at Day 28 probability to FQ and OZ439 concentration at Day 7 and baseline parasitemia.

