1.6 STATISTICAL MODIFICATIONS MADE IN THE STATISTICAL ANALYSIS PLAN

The primary efficacy population will be the PK/PD population instead of the mITT population stated in the protocol.

A per-protocol [PP] population was added in order to align the analysis population with the primary endpoint of the study. All populations have been further clarified from the protocol definitions

The derivation of the secondary endpoint, Fever clearance time (FCT), has been added. FCT will be assessed by measuring the time from the first dose until the first time that the body temperature dropped and remained <37.5 °C.

Time to 50% parasite reduction (T_{PC50}) will also be calculated in addition to the time to 99% PR.

The evaluation of the relationship between parasitemia (as measured on thick blood film and/or by qPCR) and concentration of OZ439/FQ may be performed in a separate analysis pooling data from different studies and be reported in a separate report.

The terminal half-life ($t_{1/2}$) for OZ439 and ferroquine will not be estimated as this endpoint does not contribute to the objectives of the study.

The definition of baseline to be used for efficacy analyses has been clarified.

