2.4.6 Analyses of pharmacokinetic and pharmacodynamic variables

2.4.6.1 *Analyses of pharmacokinetic variables*

Descriptive statistics and listings

All summaries/plots of PK parameters will be based on the PKPD efficacy population.

Separate summaries based on the PK population may be provided if considered useful (if PK and PKPD efficacy populations are different).

Pharmacokinetic parameters of ferroquine, its metabolite SSR97213 and OZ439 compounds will be summarized by descriptive statistics (such as arithmetic mean, geometric mean, median, SD, SEM, CV, minimum, and maximum) for each group (FQ alone, FQ/OZ439).

Box-and-whisker plots will be provided for each treatment group and compound (FQ, SSR97213 and OZ439), representing mean, median, quartiles and outlying observations.

Individual metabolic ratios (FQ/SSR97193 considering molecular weight of each moiety) will be computed for C_{max} , $AUC_{0\text{-Day}28}$ and AUC listed and summarized for each treatment group.

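### As worded, the primary population excludes the whole FQ-alone arm: it requires an OZ439 PK sample, and none is scheduled in Arm A

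*SAP*

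**What the plan says.** The SAP changes the primary population. Section 1.6 states: "The primary efficacy population will be the PK/PD population instead of the mITT population stated in the protocol". Sections 2.3, 2.3.5.1 and 2.4.4 repeat that the primary exposure-response analysis uses the PK/PD efficacy population.

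Section 2.3.5.1 builds that population from patients in both the PK and mITT sets, then adds criteria. The first is: "Patients need at least one evaluable blood sample for PK of both OZ439 and FQ". It has no exception by arm.

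The note on the OZ439 PK row reads "Not measured in Arm A; Plasma samples" in the protocol's schedule of activities (section 2), and the SAP flow chart (Appendix A) has the same note.

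Three other places read differently from the two-drug condition:

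- The SAP's PK population (2.3.4) needs only "at least one evaluable blood sample for PK of either OZ439 or FQ post IMP administration".
- The protocol's PK/PD population (section 10.2, Table 7) is simply "All participants included in both the mITT population and the PK population".
- SAP 2.4.6.1 says "All summaries/plots of PK parameters will be based on the PKPD efficacy population", then lists FQ alone as one of the groups to be summarised.

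The sample size case in SAP 1.3 is "for 4 arms FQ 400 mg + OZ439 at 0, 300, 600, and 1000 mg".

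**The concern.** The primary objective is to show what OZ439 adds to the combination. Arm A holds the only patients with no OZ439, so it anchors the exposure-response curve at zero, and it is the arm with the most expected failures. Protocol section 5.5 itself argues that including the extreme doses, 0 and 1000 mg, helps the analysis.

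Applied literally, the two-drug condition removes that arm. The primary test would then compare exposures only among patients who all received OZ439, with far fewer failures to inform the model. The sample size was not justified for that analysis.

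SAP 2.4.4.1.1 does not repair this. It names OZ439 AUC as a model variable but does not say what value an Arm A patient takes. Left missing, that covariate would drop the patient from a complete-case logistic fit even if the population definition were corrected.

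**Working it through.** **1. Who can qualify.** The condition needs an evaluable sample for OZ439 and for FQ. Arm A has scheduled FQ samples and no scheduled OZ439 samples, so its expected contribution is 0 of 30 evaluable patients.

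**2. Patients and failures.** Inputs: 30 evaluable per arm and response rates of 72%, 81%, 91% and 97% (protocol Appendix 8, SAP 1.3).

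- Four arms: N = 4 × 30 = 120; failures = 30 × (0.28 + 0.19 + 0.09 + 0.03) = 17.7.
- Arms B to D: N = 3 × 30 = 90; failures = 30 × (0.19 + 0.09 + 0.03) = 9.3.
- Arm A alone supplies 30 × 0.28 = 8.4 failures, and 8.4 / 17.7 = 47%.

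**3. Sample size arithmetic.** 30 / 0.85 = 35.3 per arm and 120 / 0.85 = 141.2 in total. This agrees with the stated approximate figures of 35 and 140, which count all four arms.

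**4. Power.** The model is eq 2 of the plan:

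logit(p) = 3.23 + 0.12 × FQ Day 7 concentration + 0.73 × OZ439 Day 7 concentration − 1.27 × log10 parasitemia

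Parasitemia on the log10 scale is normal with mean 4 and SD 0.55, truncated to 3.48–5.5. Each simulated trial is fitted with the same three covariates. The OZ439 coefficient counts as significant if its Wald z exceeds 1.96, which is the two-sided 5% test in the positive direction.

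The documents do not give the concentration distributions. I assumed log-normal concentrations with means calibrated to the 72/81/91/97% rates, coefficients of variation (CV) of 0.3–0.7 for FQ and 0.3–1.3 for OZ439, and correlation 0.2–0.4 (the plan says only that it is slight). Arm A enters with OZ439 exposure 0. Each setting used 3,000 or 5,000 trials; at 3,000 the simulation standard error near 50% is √(0.25 / 3000) = 0.9 points.

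| FQ CV | OZ439 CV | Corr. | 4 arms, 30 each | B–D, 30 each | B–D, 40 each | B–D, 60 each |
|---|---|---|---|---|---|---|
| 0.3 | 0.3 | 0.2 | 0.910 | 0.480 | 0.712 | 0.914 |
| 0.3 | 0.7 | 0.2 | 0.915 | 0.475 | 0.743 | 0.961 |
| 0.3 | 1.0 | 0.2 | 0.886 | 0.457 | 0.750 | 0.968 |
| 0.5 | 0.3 | 0.2 | 0.928 | 0.509 | 0.728 | 0.931 |
| 0.5 | 0.5 | 0.2 | 0.933 | 0.540 | 0.757 | 0.961 |
| 0.5 | 0.7 | 0.2 | 0.936 | 0.503 | 0.775 | 0.970 |
| 0.5 | 0.7 | 0.4 | 0.921 | 0.494 | 0.764 | 0.974 |
| 0.5 | 1.0 | 0.2 | 0.910 | 0.506 | 0.785 | 0.975 |
| 0.5 | 1.3 | 0.2 | 0.882 | 0.472 | 0.759 | 0.977 |
| 0.7 | 1.0 | 0.3 | 0.922 | 0.507 | 0.790 | 0.983 |

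The four-arm column, 88.2% to 93.6%, reproduces the stated power of around 90%. Without Arm A the range is 45.7% to 54.0%. A separate run with FQ CV 40% and OZ439 CV 40–100% gave 0.89–0.92 with Arm A and 0.50–0.52 without.

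The loss is not only one of numbers. With the total held at 120 in three arms (40 each), power is still only 71% to 79%. Of the sizes tried, only 60 per arm brought all ten settings back above 90%.

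**The case against.** The strongest reply is that this is a drafting slip that nobody would apply. PK summaries on this population list an FQ-alone group, SAP 2.4.1 summarises the population by treatment group, and the power case has four arms. Arm A was plainly meant to be included. I agree about the intent. But the SAP is the specification for the primary test, and the sentence that decides entry says the opposite. The trial is open label, so reinterpreting the primary population once outcomes by arm are known would be hard to defend.

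Second, it is too strong to say that OZ439 can never be sampled in Arm A. Samples before early rescue (protocol 7.7.1) and at QTcF or ALT events (schedule footnote, section 9.2) are described for both drugs with no arm limit. This stands as a point of wording, but it makes matters worse: Arm A patients would then enter mainly because they failed treatment or had a safety event, which is selection on outcome.

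Third, the dose-response regression for PCR-corrected ACPR runs on the mITT population and keeps all four arms (SAP 2.4.4, 2.4.4.1.3). That is a real but partial mitigation. It addresses a secondary objective and does not restore the primary exposure-response test.

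Fourth, the power figures rest on assumed concentration distributions. Like Appendix 8, they use Day 7 concentration, whereas the planned predictor is AUC with covariates chosen by fit statistics. Appendix 8 calls its own results approximate. The exact percentage is therefore uncertain, but the fall to about half was stable in every setting tried.

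**Conclusion.** The concern holds and must be fixed before database lock. The literal rule contradicts the sampling schedule and removes a randomized arm from the primary analysis. It takes away 30 of 120 evaluable patients and 47% of expected failures. It also cuts power from about 90% to roughly 50%, given the plan's coefficients and response rates and the assumed log-normal exposures. The contradiction itself needs no assumptions; only the size of the power loss does. Two gaps have to be closed: the entry condition, and the missing OZ439 AUC value for patients who received none.

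**What to change.** - **SAP 2.3.5.1:** replace the two-drug condition. Require at least one evaluable post-dose FQ sample in every arm and, for patients who received OZ439, at least one evaluable OZ439 sample. Tying the rule to drug received, rather than to randomized arm, avoids assigning zero exposure to an Arm A patient given OZ439 in error; the PK/PD efficacy exclusions, unlike the per-protocol ones, do not remove patients who received a different treatment.
- **SAP 2.4.4.1.1:** state that OZ439 AUC is 0 in the primary model for patients who received no OZ439, which covers Arm A, and that unscheduled OZ439 samples in Arm A do not affect eligibility.
- **SAP summary table of statistical analyses (end of Appendix B):** it lists the per-protocol population for the primary logistic regression. Align it with sections 1.6, 2.3, 2.3.5.1 and 2.4.4 in the same revision.

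The cost is two sentences and one table entry. No new data, samples or patients are needed, and the four-arm power case then applies again.
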